9.7.2. Primary Efficacy Analysis of Metastasis-Free Survival

MFS will be evaluated for the ITT population. MFS is defined as the time from randomization to the first date of radiographic progression (assessed by blinded ICR) or death on study (death within 112 days of treatment discontinuation without evidence of radiographic progression), whichever occurs first. Radiographic assessments from both

scheduled and unscheduled assessments will be used to determine events in the primary analysis. For patients not known to have had radiographic progression or death at the time of the analysis data cutoff, MFS time will be censored at the date of the last available scan before the analysis data cutoff date for the purposes of analysis. Patients who were randomized but later confirmed to have metastatic disease before randomization by ICR assessment or patients with no postbaseline tumor assessment information will be censored on the date of randomization. Patients who initiate antiandrogen receptor agents (eg, bicalutamide, flutamide, or nilutamide) without evidence of metastasis as per ICR review will not be censored for the primary MFS analysis. The details of the censoring rules are provided in [Appendix 1](#).

Significance Level

A 2-sided alpha of 0.05 will be preserved for the primary endpoint of MFS and key secondary endpoints using the testing strategy outlined in [Section 9.7.1](#). The primary endpoint of MFS and all secondary endpoints will be analyzed when approximately 440 MFS events based on ICR occur. See [Section 5](#) for additional details.

Methodology

MFS will be compared between the 2 treatment groups using a stratified log-rank test. The strata will be PSA doubling time (< 6 months vs. ≥ 6 months) and prior or current use of a bone targeting agent (yes vs. no). Kaplan-Meier curves will be used to estimate the distribution of duration of MFS. The 50th percentile of Kaplan-Meier estimates will be used to estimate the median duration of MFS. A 2-sided 95% confidence interval will be provided for this estimate. In cases where the median is not reached as of the data cutoff, the 25th percentile and its 2-sided 95% confidence interval will be provided. The progression and censoring reason will also be summarized for each treatment arm.

The null and alternative hypotheses regarding MFS can be phrased in terms of the hazard ratio $\lambda_{ArmA} / \lambda_{ArmB}$, where λ_{ArmA} represents the hazard of death for group A (enzalutamide) and λ_{ArmB} represents the hazard of death for group B (placebo). A hazard ratio of ≤ 1 indicates that the MFS is prolonged for patients randomized to group A (enzalutamide) compared with patients randomized to group B (placebo). The null and alternative hypotheses, respectively, can be written as follows:

$$H_0: \frac{\lambda_{ArmA}}{\lambda_{ArmB}} = 1 \quad H_A: \frac{\lambda_{ArmA}}{\lambda_{ArmB}} < 1$$

The hazard ratio, $\lambda_{ArmA} / \lambda_{ArmB}$, will be estimated using a stratified Cox regression model with the same strata as above.

If the estimate of $\lambda_{ArmA} / \lambda_{ArmB} < 1$ and the results from the stratified log-rank test lead to the rejection of H_0 in favor of H_A , then it will be concluded that enzalutamide prolongs MFS compared to placebo.

To evaluate the follow-up time for MFS between the 2 treatment groups, the median follow-up time for MFS will be estimated according to the Kaplan-Meier estimate of potential follow-up, also known as “Reverse Kaplan-Meier”.⁴

Subgroup Analyses of Metastasis-Free Survival

Subgroup analyses of MFS will be performed to determine whether the treatment effect is concordant among subgroups. The same methodology as in the analysis of MFS above will be used for each subgroup. All subgroup analysis will be performed using an unstratified log-rank test and will be performed using MFS assessed by ICR. The hazard ratios and their 95% confidence intervals will be displayed in a forest plot. The following variables will be used to define subgroups:

- PSA doubling time (< 6 months, ≥ 6 months);
- Baseline use of a bone targeting agent (yes, no);
- Baseline age category at baseline (at or below median, above median);
- ECOG performance status at baseline (0, 1);
- Geographic region (North America, European Union, and rest of the world);
- Total Gleason score at baseline (≤ 7 , ≥ 8) at diagnosis;
- PSA value at baseline (at or below median, above median);
- Lactate dehydrogenase (LDH) value at baseline (at or below median, above median);
- Hemoglobin value at baseline (at or below median, above median).

Sensitivity Analyses of Metastasis-Free Survival

The following sensitivity analyses will be performed for MFS.

Modified MFS 1 - Including Progression After Alternative Therapy as an Event

A modified MFS event is defined as an MFS event with a modified censoring rule where progression after initiation of any prostate cancer treatment is also counted as an event. The stratified log-rank test will be used to compare the treatment groups. All methods from the primary efficacy analysis will be repeated. The details of the censoring rules are provided in [Appendix 1](#).

Modified MFS 2 – Including Post Treatment Death as Event

A modified MFS 2 event is defined as an MFS event with a modified censoring rule where any death (including those occurred > 112 days after treatment discontinuation) is considered as progression. Modified MFS 2 is defined as the time from randomization to the first date of radiographic progression (assessed by independent central radiology review) or death,

whichever occurs first. The stratified log-rank test will be used to compare the treatment groups. All methods from the primary efficacy analysis will be repeated. The details of the censoring rules are provided in [Appendix 1](#).

Impact of Antineoplastic Therapies

A modified MFS analysis will be performed to assess the sensitivity of MFS to antineoplastic therapy. In this analysis, patients receiving any antineoplastic therapy without radiographic evidence of metastasis will be censored at the last visit with adequate radiographic assessment prior to new antineoplastic therapy. A stratified log-rank test will be used to compare the treatment groups. The details of the censoring rules are provided in [Appendix 1](#).

MFS Based on Investigator Assessment

MFS as assessed by the investigator will also be analyzed as a sensitivity analysis. The definition of MFS and censoring rule will be consistent with primary analysis. The stratified log-rank test will be used to analyze the MFS values. Furthermore, the concordance and discordance rate between the independent central radiology review and investigator assessment will be summarized using the radiographic metastasis status by the treatment groups.

Impact of Clinical Deterioration

In this sensitivity analysis, patients who discontinue study drug primarily due to clinical deterioration (defined as drop out due to adverse event, defined by investigator) prior to protocol-defined evidence of radiographic progression will be considered as having clinical deterioration, and the date of such an event will be set as the date of study drug discontinuation. The approach used for the primary analysis of MFS will be repeated after accounting for these events. The hazard ratio and its 95% confidence interval will be reported.

In addition to these sensitivity analyses, the time to tumor assessment visits will be summarized by treatment groups using the median and its 95% confidence interval.

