10.3.1. Primary Efficacy Endpoint Analysis: Metastasis-Free Survival

The primary efficacy endpoint is MFS using the assessment of radiographic progression by an independent, central, blinded radiology reviewer as described in [Section 9.1.1](#) and defined as the time from randomization to radiographic progression or death on study (death within 112 days of treatment discontinuation without evidence of radiographic progression), whichever occurs first. Patients not known to have had an MFS event at the time of analysis will be right censored on the date of the last available scan before the analysis data cutoff date for the purposes of analysis. Both scheduled and unscheduled radiographic imaging will be considered in the determination of radiographic events. The detailed conventions for censoring for the primary analysis and sensitivity analyses that incorporate possible sources of competing risk for assessment of progression will be described in the statistical analysis plan.

[figure not shown]
The MFS analysis will be performed when approximately 440 MFS events are observed. The primary endpoint analysis will be performed using a stratified log-rank test to compare the 2 treatment groups using a 2-sided test at the 0.05 level of significance.

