Appendix 1: Definition of Metastasis-Free Survival

Metastasis-free survival (MFS) is defined as time from randomization to radiographic progression as assessed by blinded independent central radiology review or death on study (death within 112 days of treatment discontinuation without evidence of radiographic progression), whichever occurs first.

The following table summarizes the protocol-specified rules for the radiographic evidence of progression (protocol version 4.0):

Tissue Type	Method of Assessment	Schedule	Comment
Bone	A whole-body radionuclide bone scan will consist of 5 regions including skull, thorax, spine, pelvis, and extremities. Radiographic progression for bone disease is defined as the appearance of 1 or more metastatic lesion on bone scan. When bone lesions are found in a single region, confirmation with a second imaging modality (plain film, CT, or MRI) will be required. Appearance of metastatic lesions in 2 or more of the 5 regions on a bone scan will not require confirmation with a second imaging modality.	Screening and every 16 weeks thereafter (earlier if progression is clinically suspected) until radiographic progression is confirmed by independent central radiology review	All study films should be read locally at the study site and submitted to the central imaging unit for independent central radiology review
Soft Tissue	Assessment of soft tissue disease will be done by CT or MRI. Radiographic progression for soft tissue disease is defined by RECIST 1.1.		

CT, computed tomography; MRI, magnetic resonance imaging; RECIST 1.1, Response Evaluation Criteria in Solid Tumors version 1.1.

The censoring rules for the primary and sensitivity analyses of MFS are summarized in the following table:

Analysis	Censoring Rules	Date of Censoring
Primary analysis of MFS	Patients with no baseline or no postbaseline assessments	Date of randomization
	Patients who were randomized but confirmed metastatic at baseline by independent central radiology review	Date of randomization
	Patients who had no confirmed metastasis as per independent central radiology review or did not die prior to data cutoff date	Date of the last radiographic assessment prior to data cutoff date
	Patients who had no confirmed metastasis as per independent central radiology review but died after 112 days following last dose of study drug	Date of the last radiographic assessment prior to data cutoff date

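### MFS counts death on study as an event, but the rule for patients with no postbaseline scan censors them at randomization with no exception for death

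*SAP*

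**What the plan says.** **Event definition.** SAP 9.7.2 and Appendix 1 both define MFS as time to radiographic progression by blinded central review or death on study, the latter being "death within 112 days of treatment discontinuation without evidence of radiographic progression". A death needs no scan to qualify.

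**Censoring rule.** The same paragraph of 9.7.2 states that "patients with no postbaseline tumor assessment information will be censored on the date of randomization". The Appendix 1 row for the primary analysis is slightly wider: "Patients with no baseline or no postbaseline assessments", again censored at randomization. Neither mentions death.

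**Sensitivity analyses.** In Appendix 1, investigator-assessed MFS and Impact of Antineoplastic Therapies take over the primary rules. Modified MFS 1 and Modified MFS 2 repeat the row. Yet 9.7.2 defines Modified MFS 2 so that "any death (including those occurred > 112 days after treatment discontinuation) is considered as progression".

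**Lines that point towards counting the death.**
- The general censoring sentence in 9.7.2 is limited: "For patients not known to have had radiographic progression or death at the time of the analysis data cutoff".
- Appendix 1 has a separate row for late deaths: "Patients who had no confirmed metastasis as per independent central radiology review but died after 112 days following last dose of study drug".
- Protocol 10.3.1 says: "Patients not known to have had an MFS event at the time of analysis will be right censored". It leaves the detailed censoring conventions to the SAP.

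**The concern.** The two instructions give the same patient different outcomes: an event on the date of death, or a censored time of zero. A programmer can follow only one, and no sentence says which prevails. Applied literally, the censoring rule removes deaths that the definition counts from the single primary test and takes those men out of the risk set at the start. It would do the same in Modified MFS 2, the analysis meant to count every death. MFS also gates all key secondary testing under SAP 9.7.1.

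SAP 9.7.2 does promise that "The progression and censoring reason will also be summarized for each treatment arm". That would show how many patients were censored at randomization, but not how many of them had died.

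**Working it through.** **1. The plan's event target.** Schoenfeld's formula with hazard ratio 0.72, two-sided alpha 0.05, 90% power and 2:1 allocation (SAP 5) gives (1.960 + 1.282)² / [(2/3)(1/3)(ln 0.72)²] = 438.2, rounded up to 439. Power at 440 events is 90.1%. The stated 440 is reproduced and is not in question.

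**2. Do the two rules overlap?** The first scheduled postbaseline scan is week 17, day 113 (protocol Appendix 5). The earliest possible last dose is day 1 and the latest death before nominal day 113 is day 112. The gap is at most 112 − 1 = 111 days, inside the 112-day limit. So every treated man who dies before nominal day 113 without radiographic progression meets the event definition. If he had no unscheduled scan, he also meets the censoring rule.

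**3. Where the conflict recurs.**

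| Analysis | Is death an event? | No-postbaseline row |
|---|---|---|
| Primary MFS | Yes, if on study | Stated, no exception |
| Investigator MFS | As primary | Inherited |
| Impact of Antineoplastic Therapies | As primary | Inherited |
| Modified MFS 1 | Yes, if on study | Repeated |
| Modified MFS 2 | Any death | Repeated |
| Impact of Clinical Deterioration | As primary, plus adverse-event discontinuations | No rows in Appendix 1 |

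**4. How many deaths?** The documents give no count, so this is an illustration only.

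Inputs from the documents: 960 and 480 patients; 135 deaths expected at the MFS analysis (SAP 8); planning OS medians of 59.7 and 46 months (SAP 5).

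Assumptions: constant death hazard; both planning hazards scaled by one factor m so that 135 deaths occur by mean follow-up F; F of 24 to 28 months, set against an analysis about 43 months after first randomization; no unscheduled scan before death.

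m solves 960[1 − exp(−m·ln2·F/59.7)] + 480[1 − exp(−m·ln2·F/46)] = 135.

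Deaths before the scan use the same expression with F replaced by 112/30.4375 = 3.68 months.

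| F (months) | m | Enzalutamide | Placebo | Total | Share of 440 |
|---|---|---|---|---|---|
| 28 | 0.276 | 11.2 | 7.3 | 18.5 | 4.2% |
| 24 | 0.322 | 13.1 | 8.5 | 21.6 | 4.9% |

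The wider range of F = 30 to 18 months gives 17.3 to 28.7 deaths (3.9% to 6.5%).

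Entry required an estimated life expectancy of at least 12 months, so early mortality may be lower than a constant hazard implies. Halving the scaled hazard gives 9.3 deaths (2.1%) at 28 months and 10.8 (2.5%) at 24 months.

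**5. Effect on power.** At a fixed cutoff, losing 10 of 440 events lowers power from 90.1% to 89.5%; losing 20 lowers it to 88.8%.

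**The case against.** **Events obviously come first.** On this view censoring applies only to men without an event, and all that is missing is a line on precedence. The three supporting lines set out above make that the likely intention. But the SAP's censoring rules do not work that way throughout. The sentence that contains the no-postbaseline rule also censors baseline-metastatic patients whatever happens later, and Modified MFS 1 exists to count progression that the primary rules censor. Intention cannot simply be read in.

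**Other rows also censor men who later die on study.** This is true of new therapy, skeletal-related events, radiation and missed visits. In the primary analysis those rows follow an intervening event or a gap in assessment. The row at issue can apply to a man whose only event is the death that the definition counts. For Modified MFS 2 the objection stands in full: all the remaining rows compete with a definition that counts any death.

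**The overlap has an edge.** A reader might infer that every unscanned early death falls within 112 days. With the ±5-day window, a last dose on day 1 and a death on day 117, before a day-118 scan, are 116 days apart. The overlap is certain only before nominal day 113.

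**The estimate is weak.** The constant-hazard model had to be cut to about 0.3 of the planning hazard to match 135 deaths, and follow-up is assumed. It also leaves out men who missed week 17 and died later unscanned. It gives an order of magnitude only.

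**The effect is limited.** OS still counts every death, and the power loss is about one percentage point. This limits the importance of the point but does not remove the contradiction.

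**Conclusion.** The contradiction is real, sits in the primary endpoint, and should be fixed. It occurs in both 9.7.2 and Appendix 1 and is plainest in Modified MFS 2. The number affected is probably small: about 9 to 22 deaths, or 2% to 5% of 440 events. That rests on a constant hazard rescaled to 135 deaths and 24 to 28 months' mean follow-up, with the low end halving early mortality. The direction is unknown because it depends on how such deaths split between arms.

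Three stronger readings are not supported:
- **That the reported MFS result left these deaths out, or was biased.** The documents do not say which rule was programmed and give no count.
- **That 9.7.2 and Appendix 1 have identical rules.** Appendix 1 also covers patients with no baseline assessment, so a correction limited to missing postbaseline scans would be incomplete.
- **That no sensitivity analysis could recover the deaths.** Impact of Clinical Deterioration counts adverse-event discontinuations before radiographic progression and has no censoring rows of its own. The text does not settle whether it captures some of these men.

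**What to change.** MFS was analysed at the 28 June 2017 cutoff and patients were then unblinded, so rewriting the rule unconditionally could misdescribe what was run.

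1. State which rule that derivation used, and report by arm the number of deaths without a postbaseline scan.
2. If deaths were counted, correct 9.7.2 and the Appendix 1 rows for the primary analysis and Modified MFS 1, so that the no-baseline/no-postbaseline rule applies only to patients who did not die on study. In Modified MFS 2, apply it only to patients who did not die before the data cutoff.
3. If the literal rule was used, leave the description of the reported primary analysis as run and add a note. Report MFS with these deaths as events as a labelled post-unblinding supplementary analysis, not as a replacement.
4. Leave the other primary censoring rows in force, but state that a patient censored under one of them with no postbaseline scan is censored at randomization. Otherwise the last scan is the screening scan, up to 42 days before randomization, and MFS time is negative.
5. For Modified MFS 2, state how the new-therapy, skeletal-related-event, radiation and missed-visit rows rank against a death.

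Cost: one statement and one count by arm from existing data; a clause in 9.7.2 and three Appendix 1 rows, or a note and one supplementary run; and a sentence each for items 4 and 5. No new data are needed.
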